"Is there a difference in sensitivities of these modifications to detecting strabismic amblyopia versus anisometropic amblyopia?"

Hypotheses

Null hypothesis 1 (H1₀): The new crowding tests do not offer better sensitivity to inter-ocular differences in acuity in amblyopic children, than the Sonksen logMAR test (SLT).

Alternative hypothesis 1 (H1_a): The new crowding tests do offer better sensitivity to interocular differences in acuity in amblyopic children, than the Sonksen logMAR test (SLT).

Null hypothesis 2 (H2₀): There is no difference in the sensitivities of the new tests to detecting strabismic amblyopia, versus anisometropic amblyopia.

Alternative hypothesis 2 (H2_a): There is a difference in the sensitivities of the new tests to detecting strabismic amblyopia, versus anisometropic amblyopia.

The following steps will be taken in order to complete this project:

- 1. Critically appraise relevant literature about the effects of crowding on visual acuity in normal and amblyopic adults and children for first-order and second-order optotypes.
- 2. Design a study to incorporate three suggested modifications to current visual acuity and crowding tests, in a sample of child control and amblyopic participants.
- 3. Statistically analyse the results, comparing those obtained on control and amblyopic children, as well as with data already gathered from normal healthy children. Data from the new tests will be compared with each other and with those obtained using the standard clinical vision test (the Sonksen logMAR Test: SLT).
- Accept or reject the given null hypotheses and discuss impact on clinical practice in a written thesis, as well as disseminate results at scientific conferences and in scientific peer-reviewed journals.

Study design, methods of data collection and data analysis

Study design

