Potential participants will have been identified by ACPOS clinicians as having anisometropic or strabismic amblyopia. Control participants of similar age will also be recruited via the ACPOS clinic as false positive referrals from the screening service. Healthy volunteers will also be acceptable as control participants. The pool of amblyopes projected for 18 months is n=278; 60% strabismic, n=167 (based on a 2016-2017 Addenbrookes audit).

As the participants will mostly have undertaken the normal screening programme and be following treatment plans as guided by the Royal College of Ophthalmology, these results should be able to be generalised to all UK 3 to 11-year-olds diagnosed with amblyopia.

Eligibility Criteria – Inclusion criteria:

- **Test participants;** Male and female 3 to 11-year-old children diagnosed by ACPOS clinicians as likely having amblyopia (strabismic or anisometropic). They will be tested following 6 weeks (or more) of refractive adaption.
- Control Participants; Male and female 3 to 11-year-old children who have been falsely referred into the Hospital Eye Service (ACPOS) by the visual screening service, or healthy volunteers who have satisfactory visual functions, as per the national screening guidelines.
- All participants must be able to complete the Sonsken logMAR Test (SLT) either verbally or via use of a matching card.

Eligibility Criteria – Exclusion criteria:

- Uncorrected refractive error.
- The presence of any other vision limiting medical condition, not listed in the inclusion criteria.
- Any prior or existing medical history of epilepsy or seizures.

Sample Size:

Based on data produced from previous studies, the outcome data obtained from this study will come from an underlying continuous and normal distribution.

As the first alternative hypothesis is two-tailed, a t-test is appropriate for the calculation of sample size, to find an estimated effect size, with standard deviations known for the visual acuity measures (Hulley and Cummings, 1988). A comparison of means during statistical analysis (Repeated Measures ANOVA) makes this a suitable strategy for determining sample size.

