The effect size is set at 0.100 logMAR, which is the minimum inter-ocular difference that should exist for the participant to be classified as amblyopic (Elliott and Firth, 2009). The standard deviation of the visual acuity measure is set as ± 0.100 logMAR. In adults, visual acuity repeatability measures of ± 0.1 logMAR have been found (Klein et al, 1983; Arditii & Cagenello, 1993; Siderov & Tiu, 1999). Lalor (2018), who used staircase procedures like those proposed, found for children aged 3 to 16 years, standard deviations of ± 0.06 logMAR. Pilot studies with the Crowding Distance Test have suggested even lower standard deviations of the test measures (Waugh et al., 2018).

Using a standardarised effect size of 1 (effect size/sd of measure; or Cohen's d of 1), a significance level or probability of committing a type 1 error (incorrect rejection of null hypothesis), of 0.05; and the probability of committing a type 2 error (incorrect acceptance of null hypothesis) of 0.2 (power of 0.8), a sample size of n=16 participants in each group

30

(amblyopes and control participants) will be required to achieve statistical significance, if a difference exists.

In brief, the data generated will be analysed using a Repeated Measures Analysis of Variance (with Huyndh-Feldt correction for violation of sphericity of variance). In this procedure means are compared. Also post-hoc Tukey comparisons between groups can be made; or a Dunnett test comparing each group (anisometropic; strabismic) to the control group (normal controls)

The above calculation is sufficient for a comparison of means. The second hypothesis involves three distinct groups with independence of observation. An alternative way to estimate sample size is to conduct a one-way ANOVA using an effect size *Cohen's f*, is set at 0.4 (for "large" effect size) to examine for large effect sizes. Once again, the significance level or probability of committing a type 1 error is set at 0.05, and the probability of committing a type 2 error is set at 0.2, to yield a study power of 80%.

Following this power calculation, a sample size of n=21 participants in each group (anisometropic amblyopes, strabismic amblyopes and control participants) will be required to achieve statistical significance, if a difference exists.

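### The plan would accept a null hypothesis on a non-significant result, but 21 v 21 cannot support a conclusion of no difference between amblyopia subtypes

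*Combined protocol and SAP*

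**What the plan says.** The Hypotheses section words null hypothesis 2 (H2) as a flat statement of equality: "There is no difference in the sensitivities of the new tests to detecting strabismic amblyopia, versus anisometropic amblyopia". Null hypothesis 1 (H1) says that the new tests are no better than the Sonksen logMAR Test (SLT) at showing inter-ocular differences in amblyopic children; its alternative says that they are better. The list of project steps that follows ends with: "Accept or reject the given null hypotheses and discuss impact on clinical practice in a written thesis".

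The Sample Size section glosses a type 2 error as "incorrect acceptance of null hypothesis". It presents 16 and 21 per group as the numbers needed for significance where there is a difference, without repeating at that point that this holds only for the assumed effect. H1 is sized as 16 amblyopes against 16 controls at a standardised effect of 1. H2 is sized by a one-way ANOVA with f = 0.4, chosen "to examine for large effect sizes".

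The planned analysis is repeated-measures ANOVA with Tukey or Dunnett comparisons. Bland-Altman analysis is planned for agreement between tests but is not linked to either hypothesis. The text gives no confidence interval for the contrasts behind H1 and H2, no equivalence margin, and no rule for reading a non-significant result.

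**The concern.** Failing to reject a null hypothesis is not evidence that it is true. The plan's only stated route from results to conclusions has two outcomes, accept or reject, and the same sentence leads on to clinical practice. Taken literally, a non-significant subtype comparison becomes a finding that the new tests work equally well in strabismic and anisometropic amblyopia. A non-significant comparison with SLT becomes a finding that the new tests add nothing.

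The risk is greatest for H2, because its null is a statement of no difference and the groups were sized for a large overall effect. A moderate subtype difference could be present, missed, and then reported as absent.

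**Working it through.** **1. The plan's own figures.**
- H2: three groups, f = 0.4, alpha 0.05, power 0.80. With N = 63, the noncentrality is f² × N = 0.16 × 63 = 10.08 on 2 and 60 df. Power is 79.8% and the exact requirement is 63.3 in total (21.1 per group). The stated 21 per group is reproduced within rounding.
- H1: n = 2 × (1.96 + 0.842)² / 1² = 15.7, so 16 per group by the normal approximation. This is also reproduced.

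The sample-size arithmetic is not in dispute.

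**2. What f = 0.4 powers.** If the two amblyopic groups have the same mean and controls differ from both by δ (in SD), then f = δ√2/3. Setting f = 0.4 gives δ = 0.4 × 3/√2 = 0.85 SD. The planned effect can therefore arise with no subtype difference at all. The calculation does not specifically power the subtype contrast.

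**3. Power of the subtype contrast, 21 v 21, two-sided 0.05.** Noncentral t with 40 df, critical value 2.021, noncentrality d × √(21/2) = 3.240d. For Tukey with three groups and 60 df, the critical value is 3.399/√2 = 2.403.

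| True difference (SD) | Power, unadjusted | Power, Tukey | Missed, unadjusted |
|---|---|---|---|
| 0.5 | 35% | 23% | 65% |
| 0.8 | 72% | 58% | 28% |
| 1.0 | 89% | 80% | 11% |

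The difference detectable with 80% power, unadjusted, is 0.89 SD. About 64 per group would be needed for 0.5 SD.

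**4. What a non-significant result would exclude.** The 95% half-width is t(0.975; 40) × √(2/21) = 2.021 × 0.3086 = 0.62 SD. The plan states: "The standard deviation of the visual acuity measure is set as ± 0.100 logMAR". It supports this with repeatability and staircase figures. The spread of inter-ocular differences among amblyopic children is not given, so the SDs above 0.10 below are assumptions.

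| SD (logMAR) | 95% half-width (logMAR) |
|---|---|
| 0.10 (plan) | 0.062 |
| 0.141 (assumed: difference of two independent eyes, 0.10 × √2) | 0.088 |
| 0.15 (assumed) | 0.094 |
| 0.20 (assumed) | 0.125 |

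At SD 0.10, a result that just misses significance has an interval from just below 0 to about 2 × 0.062 = 0.125 logMAR.

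**5. H1 for comparison.** New test versus SLT is a within-child contrast. With all 42 amblyopes, a paired t-test has 89% power at 0.5 SD of the paired difference and detects 0.44 SD with 80% power. Within one subtype of 21, the figures are 59% and 0.64 SD. The plan gives no power calculation for this contrast; its H1 calculation compares amblyopes with controls.

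**The case against.** The strongest reply is that the sentence is one item in a list of project steps that begins with a literature review, and that 'accept' is loose wording rather than a formal decision rule. The type 2 error phrase is only a gloss in brackets. The one action tied to results, under Ethical considerations, follows a positive finding: sharing useful information with the clinical team. This is fair as to intent. However, no other rule for interpreting a null result replaces the sentence, and the Sample Size section follows the same logic.

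A second reply is that at the plan's SD, 0.5 and 0.8 SD are only 0.05 and 0.08 logMAR, while a 0.100 logMAR subtype difference has 89% power unadjusted. That is correct at SD 0.10. The same 0.100 logMAR would have 56% power at SD 0.15 and 35% at SD 0.20, and the relevant SD is not documented. Even 89% power does not turn a non-significant result into evidence of equality.

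Some stronger readings are tempting, but the documents do not support them:
- **That a significant result favouring SLT would reject null hypothesis 1.** As worded, that null includes SLT being better, so such a result lies inside it. Testing a directional claim two-sided is ordinary practice. What remains is a wording mismatch, because the Sample Size section says: "As the first alternative hypothesis is two-tailed, a t-test is appropriate for the calculation of sample size".
- **That H1 is limited to groups of 21.** It is paired and can use up to 42 children.
- **That 0.100 logMAR is the plan's meaningful difference between subtypes or tests.** The plan says: "The effect size is set at 0.100 logMAR, which is the minimum inter-ocular difference that should exist for the participant to be classified as amblyopic". That is a diagnostic threshold for one child. It does not justify an equivalence margin between groups, and a logMAR margin does not directly fit the Crowding Distance Test, which measures critical spacing.

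**Conclusion.** The point stands as one about interpretation. With 21 per subtype, a non-significant H2 result leaves a range of about 0.62 SD either side of the estimate, and a true 0.5 SD difference would be missed about 65% of the time (77% with Tukey). It cannot support a statement of no difference between subtypes. The same principle applies to H1, with less force because the paired comparison is more precise.

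The figures assume 21 evaluable children per subtype, approximate normality and a common SD. The logMAR widths depend on an SD that the plan does not give for amblyopic children. A reader might infer that the sample size is wrong or that the investigators intend to claim equivalence; the documents show neither. They show wording that permits the claim and nothing that prevents it.

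**What to change.** 1. In the last project step of the Hypotheses section, replace the accept-or-reject wording with 'reject or fail to reject', and bring the type 2 error gloss in the Sample Size section into line.
2. In the statistical analysis section, commit to reporting with a 95% confidence interval (a) the strabismic minus anisometropic contrast for each new test and (b) each new test minus SLT inter-ocular difference where the scales are comparable. State in advance whether the subtype interval is Tukey-adjusted.
3. Add that a non-significant result will be described as inconclusive over the range of its interval, not as no difference.
4. Make no equivalence claim unless the sponsor pre-specifies and justifies a margin. Do not borrow the 0.100 logMAR diagnostic threshold for this.
5. Minor wording: in the Sample Size section, say that H1 is directional and is tested two-sided.

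The change needs no extra children or measurements, only revised text and intervals from the contrasts behind the planned comparisons. The downside is that some results will have to be reported as inconclusive.

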Study Design	In this single centre study, assessment of three theoretical enhancements to visual acuity testing 1) crowding-enhanced letters, 2) crowded-enhanced contrast-modulated letters and 3) measurement of crowding distance, will be tested using clinical tests in a control group and in amblyopic children. Results from these 3 tests will be compared to each other and to those from the Sonksen logMAR Test (SLT) the current clinical standard, as measured by a clinician. Comparisons across test, and between participant groups, will enable us to determine the optimal test, or combination of tests, for detecting amblyopia. Visual acuities and crowding distance will be measured prospectively in a randomised controlled trial. Results will also be obtained in a control group, a sample of false-positive referrals to the hospital, and compared to that already obtained on normal healthy children (Waugh et al., 2018).					
	The testing will take place in a clinical room neighbouring the ACPOS (Addenbrooke's Community Paediatric Ophthalmology Service) clinic, which is hosted within the University Eye Clinic at Anglia Ruskin University (ARU).					
Study Participants	Test participants; 42 Male and female, 3 to 11-year-old children diagnosed as having amblyopia (21 strabismic and 21 anisometropic) by clinicians within Addenbrookes Community Paediatric Ophthalmology Service (ACPOS), hosted by the University Eye Clinic at Anglia Ruskin University (ARU) will be recruited.					
	Control Participants; 21 Male and female, 3 to 11-year-old children who have either been falsely referred into ACPOS (Addenbrookes Community Paediatric Ophthalmology Service) by the national vision screening service, but who are subsequently found to have satisfactory visual function; or visually healthy volunteers who have already passed vision screening will be recruited.					
	All participants must be able to perform the Sonksen logMAR Test (SLT) either verbally, or by using a matching card.					
Planned Size of Sample (if applicable)	Total participant pool: n =63 Anisometropic amblyopes n =21; Strabismic amblyopes n =21; Control group n =21.					

Follow up duration (if applicable)	This project requires one visit by each participant. However participants may choose to participate more than once (up to a maximum of 3 times) during the recruitment and testing period (within the 2 year data collection period).

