Planned Study Period	It is planned that recruitment and testing will take place over 2 year period. (See Gantt Chart for estimated project delivery dates).
Research Question/Aim(s)	This study aims to investigate whether proposed modifications to visual acuity tests will offer better sensitivity to the detection of amblyopia than the Sonksen logMAR test (SLT). It will also determine whether differences in outcomes occur for anisometropic, versus strabismic amblyopes.

FUNDING AND SUPPORT IN KIND

FUNDER(S) (Names and contact details of ALL organisations providing funding and/or support in kind for this study)	FINANCIAL AND NON FINANCIALSUPPORT GIVEN				
 Anglia Ruskin University (via The Doctoral School) [name] Director of Doctoral School Research and Innovation Development Office Anglia Ruskin University, Chelmsford [name] [contact] 	The Research Supervisor/Chief investigator ([name] [name]) has been awarded a Vice Chancellor's Studentship to provide fees and a living stipend to support a PhD student, ([name]), throughout the course of this study.				
[contact] 2) Anglia Ruskin University via Quality Related Research Funds from HEFCE (Higher Education Funding Council for England) to FST and Anglia Vision Research.	Quality Related Research Funding from HEFCE awarded to ARU has been approved for the Research Supervisor to reimburse participants' parents/carers for their time (£10 per participation visit in the form of an amazon voucher) for this project.				
[name] Deputy Dean (Research and External Income) Faculty of Science and Technology Anglia Ruskin University [name] [contact]	Quality Related Research Funding has been approved for the Research Supervisor to cover the cost of computer hardware and software required for the execution and analysis of data generated from this project.				

Contact on behalf of the Sponsor

[name], Chair of Faculty of Science and Technology Research Ethics Panel (FST FREP), Department of Psychology, Faculty of Science and Technology, Anglia Ruskin University, Cambridge [name] [contact]

ROLE OF STUDY SPONSOR AND FUNDER

The Sponsor and the Funder for this project is Anglia Ruskin University (ARU).

The Principle Investigator on this study is a PhD student ([name]) funded through an ARU Vice-Chancellor's PhD Studentship, awarded to the Chief investigator / Research Supervisor ([name] [name]). The award funds the PhD student's fees and bursary.

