In this single centre study results from the 'Enhanced Cambridge Crowding Test', 'Contrastmodulated Cambridge Crowding Test' and the 'Crowding Distance Test' in their ability to detect amblyopia will be assessed using a prospective quantitative randomised controlled design. The results obtained from the experimental groups (anisometropic and strabismic amblyopia) will be compared to Sonksen logMAR test (SLT) results (assessed and documented by the ACPOS clinicians). They will also be compared to those obtained in this study from a control group. The testing will take place in a clinical room neighbouring the ACPOS (Addenbrooke's Community Paediatric Ophthalmology Service) clinic, which is hosted within the University Eye Clinic at Anglia Ruskin University (ARU).

Study procedure

Prospective participants will be identified by their clinician at their ACPOS clinical appointment, and given participant information leaflets. Healthy volunteers will also be accepted as control participants and given participant information leaflets. All participants will be required to provide informed assent, and their parent/guardian provide written informed consent before the experiments are conducted and after the nature and consequences of the study are explained. COVID tracking consent forms The recruitment and consent process will be monitored by the Principal investigator within the University Eye Clinic at ARU.

All tests will be conducted with the child's corrective lenses if required, after consent and assent is achieved. The child's Ophthalmology clinical team will be informed of their participation by use of an addendum into the clinical notes, if recruited through the ACPOS clinic. To reduce the risk of potential exposure to COVID-19 by participants during testing, the researcher will wear an apron and a mask. The researcher, participant and parent will wash their hands upon entering the testing room (which has its own sink and sanitising soap) and wear masks (Medical F2 as per ACPOS clinical protocol). Children under 11 may choose to not wear a mask. Individual risk assessments are conducted at the time of appointment creation by ACPOS/Addenbrooke's staff. All high-risk participants and parents will NOT have appointments entered into the recruitment system. All participants are children, so risk is minimal. All equipment will be Clinell wiped before and after use. Disposable occlusive patches and social distancing will also be used throughout testing.

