The testing session is expected to take 45 to 60 minutes, depending upon the attention span and cooperation of the child; this includes regular breaks and relaxation points. It will not be possible to blind the researcher as to which group test participants have been allocated, as those patients with strabismic amblyopia will likely be easily identified due to the presence of their strabismus.

Background information will be recorded on data collection sheets (Appendix 1), and results of the vision tests are recorded as data files on the experimental/display computer. Participants need only complete one testing session, but may complete to 3 sessions over the 24 month period. Additional sessions would allow for analysis change over time. Participants

are free to decide on the length of their participation and can leave the study at any time.

Background information

Prior to testing, the following relevant clinical information will be taken from the patient's digital medical records, or measured and recorded by the PI who is a registered Orthoptist;

- 1. Age
- 2. Gender
- 3. Diagnosis and Amblyopia subtype
- 4. Identification of fellow and amblyopic eye
- Most recent SLT visual acuity result for each eye, for healthy volunteers this will be assessed by the PI.
- 6. Current refractive correction
- Stereoacuity measurement. For healthy volunteers this will be assessed by the PI to ensure inclusion criteria are met.

This information will be used to identify which group the participant will be recruited to (anisometropic, strabismic or control) and also to aid randomisation of initial testing eye within each group. The participant will also be allocated a participant number and all results will be recorded using this participant number to preserve anonymity.

Randomisation

Each group will undergo covariate adaptive randomisation using minimisation to select which eye will be examined first (Hu et al., 2014). Test participants will have either their Amblyopic eye (AE) or Fellow eye (FE) assessed first for all 3 experiments, and control participants will have either their Right eye (RE) or Left eye (LE) assessed first. This will ensure equal distribution of known confounding variables (e.g. amblyopia density, occlusion regime, gender) for testing order bias between eyes. This minimisation process will allow for better statistical analysis and extrapolation of results. The order of experiments will be counterbalanced to prevent testing order bias.

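### The clinic SLT reading helps assign the groups and is also the comparator, with no independent reference standard, so better detection than the SLT cannot be shown and the H1 comparison leans towards the SLT

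*Combined protocol and SAP*

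**What the plan says.** **Aim.** The synopsis (Research Question/Aim(s)) asks whether the modified tests "will offer better sensitivity to the detection of amblyopia than the Sonksen logMAR test (SLT)". The synopsis Study Design and the main research question also speak of detecting amblyopia.

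**Hypothesis.** H1 is narrower: "The new crowding tests do offer better sensitivity to interocular differences in acuity in amblyopic children", relative to the SLT.

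**Comparator.** Under Study design, results in the amblyopic groups "will be compared to Sonksen logMAR test (SLT) results (assessed and documented by the ACPOS clinicians)". Appendix 2 (Schedule of Procedures) lists the modified tests at the study visits but no separate SLT.

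**Grouping.** Item 5 under Background information is "Most recent SLT visual acuity result for each eye, for healthy volunteers this will be assessed by the PI". Diagnosis and subtype, refractive correction and stereoacuity are on the same list. Of the whole list the protocol says: "This information will be used to identify which group the participant will be recruited to (anisometropic, strabismic or control)".

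**Cases and controls.** Cases are "children diagnosed by ACPOS clinicians as likely having amblyopia (strabismic or anisometropic)". Clinic controls are children referred by screening "but who are subsequently found to have satisfactory visual function". Volunteers who have passed screening may also be controls.

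**Link between diagnosis and SLT.** The Background section names reduced acuity as the main criterion for diagnosing amblyopia. The Rationale names the SLT as the department's standard acuity test. The Sample Size section gives 0.100 logMAR as the smallest inter-ocular difference that should be present for a child to be classed as amblyopic.

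**The concern.** The test to be beaten helps to define the truth against which it is judged. This has two consequences.

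1. **Detection.** A new test can detect more than the SLT only in children whose amblyopia the SLT does not show. Those children are unlikely to be diagnosed and enrolled as cases. If screening referred them and the clinic found their vision satisfactory, they can be enrolled as controls. A correct positive on a new test would then look like a difference in a healthy child. No reference standard or follow-up of controls is described that could reveal this.

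2. **H1.** When a child is classed as amblyopic partly because an SLT reading showed a large inter-ocular difference, that reading carries on average some measurement error in the same direction. If it is then used as the comparator, the SLT difference in cases is inflated. In controls it is reduced by the same mechanism. The new tests are measured afresh and gain nothing from this. A real advantage for a new test would be understated, and a null result could wrongly dismiss a better test. A larger sample does not remove the bias.

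**Working it through.** **The plan's own figures.** For H1, n per group = 2 × (1.960 + 0.842)² × (0.100/0.100)² = 15.7, so 16 as stated. For three groups with Cohen's f = 0.4, the total is 63.3, or 21.1 per group; power at 21 per group is 0.798. Both figures reproduce within tolerance. The sample size is not at issue here.

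**Inputs for the bias.**
- Cut-off c = 0.10 logMAR and SDs of 0.06 and 0.10: Sample Size section. Reading the SDs as per-eye measurement error is an assumption.
- True inter-ocular difference in amblyopes, normal with mean μ = 0.2, SD τ = 0.10, or μ = 0.3, τ = 0.15: assumptions, not in the documents.
- A new test exactly as good as the SLT, with independent error.

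**Formula.** The error SD of a two-eye difference is σe = √2 × per-eye SD: 0.085 for 0.06 and 0.141 for 0.10. Let σS = √(τ² + σe²) and a = (c − μ)/σS. If children enter as cases when their SLT difference is at least c, the mean SLT error carried into the comparison is

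bias = (σe²/σS) × φ(a)/Φ(−a).

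Example, μ = 0.2, τ = 0.10, per-eye SD 0.10: σS = √(0.01 + 0.02) = 0.173; a = −0.10/0.173 = −0.577; bias = (0.02/0.173) × 0.338/0.718 = 0.054.

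The last column comes from simulation. It lets the SLT alone set the group and assumes that half of all referrals are truly amblyopic, with a floor of 0.1 on their true difference.

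| Mean, SD of true difference | Per-eye SD | Bias, all cases truly amblyopic | Bias, SLT alone sets the group |
|---|---|---|---|
| 0.2, 0.10 | 0.06 | 0.021 | 0.037 |
| 0.2, 0.10 | 0.10 | 0.054 | 0.086 |
| 0.3, 0.15 | 0.06 | 0.010 | 0.026 |
| 0.3, 0.15 | 0.10 | 0.029 | 0.063 |

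Simulating the third column with the 0.1 floor on true differences gives 0.011 to 0.054, essentially the same.

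**What this does to a real gain.** Suppose a new test truly enlarges the difference by 0.05 logMAR. With all cases truly amblyopic it would appear as 0.05 − 0.054 = −0.004 at worst and 0.05 − 0.010 = +0.040 at best.

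**Sensitivity to the assumptions.**
- Milder amblyopia (mean true difference 0.1, SD 0.10, truncated at zero) gives 0.042 to 0.086 even when all cases are truly amblyopic.
- The bias scales with the share of children whose grouping reading is also the comparator reading. If that share is one half, the SLT-alone range halves to 0.013 to 0.043.
- With an independent SLT reading as comparator, the simulated bias is zero to three decimals.

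**The case against.** Several stronger readings are tempting, and the documents do not support them.

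- **That the SLT alone decides the group.** It is one item on a list with clinician diagnosis, refraction and stereoacuity. The eligibility criteria contain no SLT cut-off; the 0.100 figure appears only in the Sample Size section. Children already under treatment are enrolled, so their diagnosis may rest on an earlier reading than the most recent SLT. For them, independent measurement error adds no selection bias. The last column of the table is therefore an upper bound for the stated scenarios.
- **That the study can answer nothing.** H1 is a within-child comparison in diagnosed amblyopes and stays estimable. So do H2 and the comparisons among the new tests.
- **That a sensitivity and specificity table will favour the SLT.** None is planned. The analysis is repeated-measures ANOVA with Bland-Altman agreement.
- **That many apparent false positives among controls would be missed amblyopes.** With half of referrals assumed amblyopic, a simulation of a test that enlarges differences by 30% gives 39 to 57%. At the 3% prevalence quoted in the Background, which fits screened volunteers better, it is about 1 to 3%. The documents do not settle which figure applies.

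The bias is also conservative for the new tests: a positive H1 result would be obtained in spite of it. In truly amblyopic cases, a test that enlarges differences by 30% still shows a larger mean than the SLT in all four scenarios, by 0.014 to 0.087 logMAR.

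These points limit the concern but do not remove it. The dual use of the reading is in the text, and nothing in the documents supplies a diagnosis independent of the SLT.

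**Conclusion.** The point holds in this form: the clinic SLT reading is a main input to grouping and is also the comparator, with no independent reference standard. The detection claim in the synopsis and the research question is therefore beyond what this design can show. H1 remains estimable, but is biased against the new tests for every child whose grouping reading is also the comparator.

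The size is about 0.01 to 0.05 logMAR if all cases are truly amblyopic, up to about 0.09 if the SLT alone set the group, and about zero with an independent reading. The planned effect is 0.1. These figures rest on assumed mean true differences of 0.2 to 0.3 logMAR, on treating the plan's SDs as per-eye error, and on a 0.10 cut-off being applied. The direction does not depend on the exact values; the size does, and milder amblyopia would make it larger.

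The asymmetry matters for interpretation. A positive H1 result would stand, but a null or small one could not be read as evidence that the new tests offer no gain.

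**What to change.** 1. **Separate the readings.** Use as the H1 comparator an SLT reading that was not used for grouping. The simplest source is a short SLT repeated at the study visit by the principal investigator, who is a registered orthoptist and already tests the volunteers. For volunteers too, it should be separate from the reading that confirms eligibility. Add it to Appendix 2 and to the counterbalanced test order. The cost is a few minutes per child in a session of 45 to 60 minutes. This has to be settled before testing, because a missing second reading cannot be recovered afterwards.

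2. **Narrow the aim and the conclusion.** State that the study compares the size of inter-ocular differences between tests in clinically diagnosed amblyopes and controls, and does not test detection of amblyopia that the SLT misses. State also that, wherever the grouping SLT remains the comparator, the bias is conservative for the new tests. The cost is wording and a narrower headline claim.

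3. **Optional, descriptive only.** Flag controls whose recorded refraction or stereoacuity suggests risk, and report control results with and without them. These data are already on the background list, and stereoacuity is already checked for volunteers. This should not become a test of detection: such a child is not proven amblyopic, and a positive new test could not be verified.

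None of these changes needs a larger sample.
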